Participants will be randomized for drug treatment order (e.g. whether they will undergo treatment with estradiol or hydrocortisone first). All study participants will undergo both drug treatments.

Table of Study Events

Procedure	Screening	Pre-treatment PK study, day 1	Pre-treatment PK study, day 2	Post-treatment PK study, day 1	Post-treatment PK study, day 2
Room #	Visit 1 CRRC	Visits 2, 6* ITHS Adult TRU	Visits 3, 7* CRRC	Visits 4, 8* ITHS Adult CRU	Visits 5, 9* CRRC
		Baseline: prior to estradiol or hydrocortisone treatment		After 1 week of estradiol or hydrocortisone treatment	
Consent/HIPAA	X				
Medical History	X				
Body weight and vital signs	X	X		X	
Physical exam	X				
Buccal swab for DNA testing	X				
Dronabinol administration		X		X	
IV catheter placement and blood draws over 12 hours		X		X	
Non-fasting blood draw	X		X		X
Urine pregnancy test	X	X		X	
Begin 24-hour urine collection		X		X	
Drug dispensing** (estradiol or hydrocortisone)			X		
Adverse event query		X	X	X	X
Payment	\$50	\$200		\$200	

*Parallel visits (6, 7, 8, and 9) will occur after the second drug treatment period.
 
**Participants will complete 7 days of treatment with either estradiol or hydrocortisone immediately following Visit 3 and Visit 7.
 
PK = pharmacokinetic
 
Pre-treatment PK visits will be scheduled on menstrual cycle days 0-3 for hydrocortisone and 15-17 for estradiol
 
An additional \$150 will be paid upon study completion for a total compensation of \$1,000
					

Primary and Secondary Objectives and outcome measures

The goal of this aim is to test *in vivo* in women the hypothesis that increased concentrations of estradiol and/or cortisol lead to increased metabolic clearance of THC. The rationale is to specifically isolate the influence of pregnancy hormones in regulating CYP-mediated THC clearance in the absence of other complicating physiological changes that occur during pregnancy. This study is unique as, unlike studies done during pregnancy that demonstrate associations, **this study will test causality**. It will specifically test whether the pregnancy hormones commonly implicated in pregnancy-mediated regulation of CYP enzymes cause an induction of CYP activity *in vivo*. The obtained data will be **critical** for developing an understanding of how THC disposition varies between individuals and in predicting how the exposures to THC and its metabolites might be altered during pregnancy

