The primary outcome measure of the study will be the change in the area under the plasma concentration-time curve (AUC) of THC following each of the interventions: exogenous estradiol and hydrocortisone exposures.

Estradiol phase:

Primary Outcome 1: Determination of whether estradiol alters THC exposure

The primary outcome is to determine whether the exposure to THC (as determined by AUC) is altered consequent to estradiol treatment when compared to the pre-treatment control and to quantify the magnitude of the change.

Secondary Outcome 1: Determination of whether other pharmacokinetic parameters of THC and its metabolites are different as a consequence of estradiol treatment

We will determine the time to peak concentration of THC, the peak concentration of THC, and the half-life of THC before and after estradiol treatment. We will also determine the AUC of metabolites of THC (11-OH-THC, 11-nor-COOH-THC, the glucuronides of 11-OH-THC and 11-nor-COOH-THC) before and after estradiol treatment. We will calculate the fraction of THC dose excreted into urine in the form of each of the metabolites and the renal clearance of each of the compounds based on urine and plasma data.

Secondary Outcome 2: Determination of the magnitude of effect of THC on heart rate in the presence and absence of estradiol treatment

As an objective measure of the pharmacologic effects of dronabinol, subjects will undergo monitoring of heart rate. The change in heart rate will be reported for each time point after dosing in comparison to baseline. The time course of change in heart rate will be reported and the change in heart rate at each time point after baseline will be compared to baseline. These data will be used as a descriptive measure of the magnitude and duration of the pharmacological effects of THC and to explore whether the doses used are pharmacologically active.

Secondary Outcome 3: Description of the side effects and psychoactive effects caused by THC in the presence and absence of estradiol treatment

Subjects will be asked to rate subjective effects related to mood, drug effect, and physical symptoms using a VAS as a function of time after dronabinol dosing. Subjects will complete VAS ratings at each of the blood sampling timepoints during the pharmacokinetic study visits.

Hydrocortisone phase:

Primary Outcome 1: Determination of whether hydrocortisone alters THC exposure

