We expect a 50% change in THC clearance to be clinically significant and, based on existing data on CYP2C9 induction by glucocorticoids and estrogens, we predict the clearance of THC to be induced by 50% in our study by one or both of the hormonal exposures. Hence, we have powered our study to detect a 25% decrease in the AUC of THC. Based on the published variability in THC and its metabolite disposition and the variability in the magnitude of drug interactions measured, a paired power calculation for 80% power with an α (Type I error rate) of 5% results a **target number of subjects of 12 for each DDI study phase**. We intend to consent and enroll 16 subjects to undergo both study phases to ensure 12 subjects who complete all study procedures and have a wild type genotype for UGT1A1 and CYP2C9.

As a secondary outcome, we will determine the effects of estradiol and hydrocortisone treatment on the AUCs of 11-OH-THC, 11-nor-COOH-THC and the 11-nor-COOH-THC-glucuronide. Of these, 11-OH-THC is an active metabolite, and it has also been shown to be much more greatly affected by rifampicin induction than THC. Based on the published variability in the exposures to the THC metabolites, 12 subjects will also provide us with adequate power to determine whether the exposures to these metabolites are altered by estradiol or hydrocortisone. The changes in AUC will be tested using analysis of variance on log-transformed data. Point estimates and 90% confidence intervals will be defined for treatment versus control in THC disposition in accordance to the guidance on statistical analysis of DDI studies. To establish the difference between treatment and control, % confidence interval of the geometric means must be outside of the range of 0.80 to 1.25. If any of our subjects have a CYP2C9*2,*3 and UGT1A1*28 genetic polymorphism, we will also analyze the data for subjects with the specific genotype separately to avoid variability introduced by genetic polymorphisms.

3. Trial Management

The procedures will be conducted within the UW Institute of Translational Health Sciences (ITHS) Adult Translational Research Unit (TRU) and the UW Center for Research in Reproduction and

Contraception (CRRC), both of which are housed within the University of Washington Medical Center (hospital). There will be no other clinics or data collection centers involved.

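### Enrolling 16 unselected women does not secure 12 completers who are wild type at both UGT1A1 and CYP2C9, and the primary analysis set is not defined by genotype

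*Combined protocol and SAP*

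**What the plan says.** Section 2, Sample size and power calculation, states the effect to be detected ("we have powered our study to detect a 25% decrease in the AUC of THC") and arrives at a "target number of subjects of 12 for each DDI study phase". The variability behind this is described but not given as a number: "Based on the published variability in THC and its metabolite disposition and the variability in the magnitude of drug interactions measured". The section then sets enrolment at 16, "to ensure 12 subjects who complete all study procedures and have a wild type genotype for UGT1A1 and CYP2C9". It foresees that women with CYP2C9*2, CYP2C9*3 or UGT1A1*28 will be among those enrolled, and says of them that "we will also analyze the data for subjects with the specific genotype separately to avoid variability introduced by genetic polymorphisms".

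Other parts of the document bear on this:

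- Section 2, Inclusion and Exclusion Criteria: inclusion items a to e and exclusion items a to r do not mention genotype.
- Section 2, Table of Study Events: "Buccal swab for DNA testing" is marked at screening, but no rule uses the result to exclude or replace anyone.
- Section 3, Table 2: cumulative enrolment ends at 16.
- Section 4, Statistical analysis plan: paired analysis of variance on log AUC, each woman her own control, with no restriction by genotype.

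**The concern.** The number that carries the power statement is 12, and the enrolment sentence describes those 12 by two conditions: completion and wild type at both genes. Only completion is partly under the trial's control. Without genotype-based entry or replacement, the number of double-wild-type completers among 16 is left to chance, and the documents offer no frequency from which to judge that chance.

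The sample-size section counts wild-type completers, while the analysis section names no genotype-defined set. Both an all-completer and a wild-type-only primary analysis remain open, so the choice could be made after the results are known. With 12 to 16 women and a conclusion that depends on where a confidence interval lies relative to 0.80 to 1.25, that choice could alter the finding.

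**Working it through.** **Inputs from the documents.** Target 12 per phase; enrolment 16; power 80%; type I error 5%; AUC ratio 0.75, so the log ratio is ln(0.75) = −0.288.

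**Inputs not given, hence assumed.**

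- Sidedness: two-sided, because the outcome is "whether the exposure to THC (as determined by AUC) is altered consequent to estradiol treatment".
- SD of the within-woman log difference: back-solved below.
- Joint probability q = P(completes) × P(wild type at both genes), treating the two as independent: shown as a range.

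**Step 1: the plan's 12.** Paired t-test power on log AUC comes from the noncentral t distribution with n − 1 degrees of freedom and noncentrality |ln 0.75| × √n / SD. Setting n = 12 and power = 80% gives SD = 0.324 (noncentrality 0.288 × √12 / 0.324 = 3.08). A one-sided test would imply 0.375. The 12 is therefore attainable but cannot be verified. A two-sided test would need 9 women at SD 0.25, 14 at 0.35 and 18 at 0.40.

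**Step 2: the plan's 16.** 12 / (1 − 0.25) = 16. The allowance is 4/16 = 25% for every loss combined.

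**Step 3: chance of 12.** With X ~ Binomial(16, q), the chance of meeting the stated aim is P(X ≥ 12). The last column applies only if the primary analysis were restricted to wild-type completers. It averages the two-sided paired-t power over the distribution of X at SD 0.324.

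| q | Expected number, 16q | P(X ≥ 12) | Average power, wild-type completers only |
|---|---|---|---|
| 0.90 | 14.4 | 98% | 87% |
| 0.80 | 12.8 | 80% | 82% |
| 0.75 | 12.0 | 63% | 79% |
| 0.70 | 11.2 | 45% | 75% |
| 0.60 | 9.6 | 17% | 67% |
| 0.50 | 8.0 | 4% | 56% |

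Solving P(X ≥ 12) = 0.90 gives q of about 0.84, and 0.95 gives about 0.87. If 90% of women complete, the 0.84 requires 0.84 / 0.90 = 93% of those enrolled to be double wild type.

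**Step 4: all completers analysed.** Genotype then removes nobody. At 90% completion the chance of at least 12 is 98%. At the same SD, power is 80% with 12 completers and 87% with 14.

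**The case against.** A reader might infer that the analysed sample and its power collapse. The documents do not support that. No text confines the primary analysis to wild-type women. The genotype-specific analysis is introduced with the word also, which describes an addition, and the analysis plan applies no genotype filter. On that reading all completers are analysed, and the step from 12 to 16 already works as a dropout allowance.

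Three further points have force:

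- **Missing 12 is not the same as losing the study.** At q = 0.70 the chance of 12 is only 45%, yet average power is 75%, about 5 points below the stated 80%. A large loss needs a low q, which nothing in the documents establishes.
- **The SD of 0.324 is inferred.** It is also held fixed for wild-type women, whereas the plan's reason for separating genotypes is to reduce variability. With 8 women, power is 58% at 0.324 but about 80% at SD 0.25 and 70% at 0.28.
- **Pairing does not remove every genotype effect.** A constant proportional effect on AUC cancels in the log ratio, but a difference in induction between genotypes does not. The plan cites variability in the size of interactions, so its interest in genotype is not refuted.

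These points limit the size of the problem. They do not rescue the claim that 16 ensures 12, and they do not settle which set is primary. Section 5 bars only omissions based on subjective assessment, so it does not rule out a restriction by genotype.

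**Conclusion.** The sample-size statement is wrong as written: 16 women enrolled without regard to genotype do not ensure 12 double-wild-type completers. Even at exactly the 25% joint loss that the allowance implies, the chance of reaching 12 is 63%.

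The effect on power is conditional on a wild-type-only primary set, which the plan does not state; on q, for which it gives no basis; and on an SD of 0.324, two-sided and unchanged in wild-type women. Under those conditions average power runs from about 82% at q = 0.80 to 56% at q = 0.50. If all completers are analysed, genotype costs no sample. What is firmly established is an unsupported enrolment figure and a primary set left open on genotype.

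**What to change.** 1. In the sample-size section, remove the wild-type condition from the 12-completer target and describe 16 as an allowance for 25% dropout.
2. In the statistical analysis plan, define the primary set in each phase as all participants with an evaluable pre/post pair in that phase, whatever their genotype.
3. Report the wild-type-only ratio as a sensitivity analysis, and show individual ratios by genotype descriptively in place of separate genotype analyses.

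The cost is wording and one small extra analysis. There is a small downside: if induction differs by genotype, the primary ratio is an average over genotypes and its variability may be larger. The sensitivity analysis would show this.

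If wild-type women are the intended primary population, the plan should instead use the genotype from the screening swab for entry and drop the claim that 16 unselected women ensure 12. That is a change of design, and the plan should then state the genotype frequencies and dropout it assumes.

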Table 2. Planned Enrollment table. We anticipate initiation of participant recruitment and enrollment roughly midway through Year 1, and we plan to complete enrollment during Year 4. All subjects will undergo sequential treatment with estradiol and hydrocortisone, with pre- and post-treatment doses of dronabinol for each hormone exposure. Subjects will be randomized to treatment order.

Grant year	Number of subjects enrolled during the year	Cumulative number of subjects enrolled
Year 1	3	3
Year 2	4	7
Year 3	5	12
Year 4	4	16
Year 5	0	16

Healthy, 21-45-year-old premenopausal, non-pregnant female volunteers will be enrolled to complete the study. Since the research is focused specifically on THC exposure during pregnancy, only women will be enrolled in the study. In addition, estradiol is approved for use only in women. Dronabinol is only approved for use in adults. Therefore, we will not recruit individuals under the age of 21. At present the psychological and developmental risks of dronabinol use in children are unknown.

We ask study subjects to volunteer information about their race and ethnicity, but this information is not required for participation in our studies. Our previous clinical research studies have had the following demographic distribution: 85% of our study subjects are Caucasian, 5% are African-American, 7.5% are Asian and 1% each Native American and Hispanic. This breakdown closely reflects the demographics of our community, and we remain committed to increasing enrollment of underrepresented minorities in our studies.

4. Data Management

Statistical analysis plan

The changes in AUC of THC after treatment with either estradiol or hydrocortisone will be tested using paired analysis of variance on log-transformed data with each subject serving as her own control. Point estimates and 90% confidence intervals will be defined for treatment versus control in THC disposition in accordance to the guidance on statistical analysis of DDI studies. To establish a difference between treatment and control, % confidence interval of the geometric means must be outside of the range of 0.80 to 1.25. This statistical analysis is concordant with the FDA guidance on analysis of drug-drug interaction data.

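### The rule for establishing a difference in THC AUC (confidence interval outside 0.80 to 1.25) is not tied to the calculation that gave 12 subjects; read literally, its power at a 25% decrease is about 14% to 16%, not 80%, under a back-solved SD

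*Combined protocol and SAP*

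**What the plan says.** The primary question in each phase is about any change in exposure. For estradiol it is "to determine whether the exposure to THC (as determined by AUC) is altered consequent to estradiol treatment", together with how large the change is; the hydrocortisone phase is worded in parallel.

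Under Sample size and power calculation, the investigators write "we predict the clearance of THC to be induced by 50% in our study" and then "we have powered our study to detect a 25% decrease in the AUC of THC". A paired calculation at 80% power and a 5% type I error rate yields a "target number of subjects of 12 for each DDI study phase". That calculation mentions no margin, no SD and no sidedness.

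The same section goes on to the decision: "To establish the difference between treatment and control", the "confidence interval of the geometric means must be outside of the range of 0.80 to 1.25". Section 4, Statistical analysis plan, repeats the rule for THC AUC after stating that the changes will be tested by paired ANOVA on log-transformed data and reported with 90% confidence intervals. In both places the number before the percent sign in the rule is absent from the text I have. I do not treat that as an error.

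**The concern.** A paired calculation with no margin is naturally read as a test of a geometric mean ratio of 1. The rule asks for more: for a decrease, the upper confidence limit must fall below 0.80. The design ratio of 0.75 lies 0.288 log units from 1 but only 0.065 from 0.80, so the rule discards about 78% of the distance on which the sizing rests (1 − 0.0645/0.2877).

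The plan also does not say what is concluded if the paired ANOVA is significant but the interval overlaps 0.80. Both primary outcomes turn on that. With the rule applied as worded, a real 25% decrease would usually be reported as no difference established.

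**Working it through.** **Inputs from the plan:** n = 12 completers, 80% power, alpha 5%, ratio 0.75 (ln = −0.2877), bounds 0.80 and 1.25 (ln 0.80 = −0.2231). **Assumed:** a 90% interval, from the sentence before the rule; a power calculation against a ratio of 1.

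**1. The plan's own figure.** Without an SD, n = 12 cannot be reproduced, so I solved for the SD of the paired log difference that yields it (paired t test, 11 df, noncentral t).
- Two-sided 5%: critical value 2.201; 80% power needs noncentrality 3.078. SE = 0.2877/3.078 = 0.0935; SD = 0.0935 × √12 = 0.324. Within-subject CV = √(exp(0.324²/2) − 1) ≈ 23%.
- One-sided 5%: critical value 1.796; noncentrality 2.655. SE = 0.2877/2.655 = 0.1084; SD = 0.375.

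**2. Literal rule, whole 90% interval below 0.80.** Power = P(T > 1.796), where T is noncentral t with 11 df and noncentrality ln(0.80/ratio)/SE. The chance of lying wholly above 1.25 is negligible at these ratios.
- Ratio 0.75: ln(0.80/0.75) = 0.0645. 0.0645/0.0935 = 0.69, power 16.0%. 0.0645/0.1084 = 0.60, power 13.9%.
- Ratio 1/1.5 = 0.667 (clearance up 50%, bioavailability unchanged): ln(0.80/0.667) = 0.1823. 0.1823/0.0935 = 1.95, power 57%. 0.1823/0.1084 = 1.68, power 47%.

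At ratio 0.75 and SD 0.324, simulation has the interval straddling a bound in 83% of trials. If the level were 95%, power at 0.75 would be 9%.

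**3. Not wholly inside 0.80 to 1.25, used alone.** By simulation at SD 0.324, a difference is declared in about 99% of trials at ratio 0.75, but also in about 55% at ratio 1.

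**4. Dependence on the SD (n = 12, 90% interval).**

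| SD of log difference | Two-sided 5% paired test, ratio 0.75 | Literal rule, 0.75 | Literal rule, 0.667 | Not wholly inside, ratio 1 (false positive) |
|---|---|---|---|---|
| 0.20 | >99% | 28% | 90% | 5% |
| 0.25 | 95% | 21% | 76% | 21% |
| 0.30 | 86% | 17% | 63% | 44% |
| 0.324 | 80% | 16% | 57% | 55% |
| 0.375 | 68% | 14% | 47% | 74% |
| 0.50 | 44% | 11% | 32% | 95% |

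The literal rule reaches 80% at ratio 0.75 with 12 subjects only if the SD is about 0.084 (within-subject CV about 6%).

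**5. Completers for 80% power under the literal rule, SD 0.324:** about 157 at ratio 0.75 and 21 at 0.667, against 12 required and 16 to be enrolled.

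**6. Combined reading: paired ANOVA significant at two-sided 5% and the interval not wholly inside.** At SD 0.324, simulation gives about 80% power at ratio 0.75 and 4.8% false positives at ratio 1.

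**The case against.** The strongest reply is that the paired ANOVA is in the plan and keeps its 80% power. The rule can be read as an added condition on it, and step 6 shows that this combined reading nearly reproduces the stated 80% and 5%. So a reader who infers that no reading of the plan delivers its power and error rate goes too far. What stands is that the words of the rule do not naturally say this: an interval that must be outside a range is not one that merely fails to sit inside it, and nowhere are the two criteria combined or ranked.

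A reader might also infer that the trial's power simply is 16%. The documents do not support so flat a statement. They give no SD, sidedness or stated null for the calculation, and the 90% level is carried over from the neighbouring sentence. The figure is conditional on these, although no SD between 0.20 and 0.50 brings power at 0.75 above 28%.

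Nor can one say that the looser reading usually produces false claims. That holds at the back-solved SDs but not at 0.20 to 0.30 (5% to 44%). Likewise, failure is not the likelier outcome at every effect the plan has in view: at the predicted clearance change the literal rule succeeds in 57% of trials at SD 0.324, though only 47% at 0.375.

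Finally, requiring a change beyond 20% is a legitimate aim, and the plan cites FDA guidance for its analysis. The geometric mean ratio and its interval also serve the aim of quantifying the change under any rule. Neither point reconciles the rule with the sample size.

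**Conclusion.** The point holds in this form: the criterion for establishing a difference is ambiguous, is not the criterion for which 12 subjects were derived, and on its literal wording does not deliver the stated power. The shortfall at a 25% decrease is from 80% to about 14% to 16%, given the back-solved SDs, a 90% interval and a power calculation against a ratio of 1. The shortfall itself does not hinge on the exact SD, since the rule would need one near 0.084. The 47% to 57% at a ratio of 0.667 further assumes unchanged bioavailability. The 80% is not refuted for the paired ANOVA taken alone. Because the sentence governs both primary conclusions, it should be settled before the data are analysed.

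**What to change.** In both sections, state that the primary decision for each hormone is the planned paired ANOVA of log AUC against a geometric mean ratio of 1 at two-sided 5%. This is the test consistent with the sizing. Report the ratio with its 90% confidence interval. Use 0.80 to 1.25 only to describe size: interval inside, no relevant change; wholly outside, a change beyond the bound; straddling, size inconclusive.

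Give the SD and sidedness behind the 12 subjects. If the calculation was one-sided, the two-sided test has about 68% power at ratio 0.75 (noncentrality 2.655 against a critical value of 2.201, 11 df), and the plan should say so.

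Alternatively, keep the literal rule and replace the 80% with its own power, showing the SD assumption. Keeping both the rule and 80% power would need more completers, as in step 5.

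The preferred change is to wording only and adds no subjects, visits or samples. Its cost is scientific: a positive result would show that exposure is altered, not that it is altered by more than 20%.
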